#### **Immune-Profiling Studies**

- 1. T cell function will be assessed for changes in multiple characteristics including memory formation, TH-polarity, markers of exhaustion, and activation via flow cytometric analysis. Naïve and memory sub-populations will be defined according to expression of CD45RA, CD62L, CCR5 and CCR7. TH-polarization, including TH1, TH2, TH17 and Treg subsets, will be determined by intracellular cytokine and FoxP3 profiles. Changes in T cell exhaustion phenotype will be tracked in terms of surface expression of several well-defined markers, including CD160, CD200R, CD244, CD272, CD274, CD279, as well as the intracellular markers Lag3 and Tim3. Alterations in cellular activation will be measured in terms of phosphorylation of critical T cell signaling pathways, STAT 1, 3 and 5, as well as by surface expression of CD107a, correlating to secretory/cytotoxic activity.
- 2. Global Immune function will be assessed. A) Patient peripheral blood will be assessed by multi parameter flow analysis for myeloid cells—specifically myeloid derived suppressor cells MDSCs both PMN-MDSCs and M-MDSCs using the following markers: CD3, CD14, CD19, CD56 HLA-DR, CD33, CD15, CD66b, and CD11b. B) Patient sera will be evaluated by flow cytometric means using cytokine bead arrays to measure serum cytokine levels quantitatively. The cytokine panel

will include IFN- $\gamma$ , TNF- $\alpha$ , IL-2, IL-4, IL-10, IL-6, IL-17A, allowing discrimination between TH1, TH2, and TH17 profiles.

- 3. Peripheral blood to collect DNA and RNA will be processed for future assessments.
- 4. Pharmacodynamics analysis of pAKT expression (Phos-Flow) for collected samples over time point of continued study.

# 5 6 TREATMENT PLAN

#### 6.1 TREATMENT SUMMARY

Treatment will be administered on an outpatient basis in 4-week (28 day) cycles.

#### Umbralisib

- 6.1.1 800 mg umbralisib once daily within 30 minutes of a meal until removal from study
- 6.12- Patient diary will be utilized

#### 6.2AGENT ADMINISTRATION

Umbralisib will be self-administered orally, all on an outpatient basis.

#### 6.2.1 GUIDELINES FOR ADMINISTRATION OF UMBRALISIB

• *Method of Administration:* Umbralisib will be administered orally once daily within

30 minutes of a meal.

- *Potential Drug Interactions*: No drug interactions have been reported to date.
- *Anti-microbial prophylaxis:* Patients are required to start prophylaxis treatment with pneumocystis jiroveci pneumonia (PCP) and antiviral therapy prior to Cycle 1, Day 1.
  - *Anti-viral Prophylaxis*: Valtrex 500 mg daily or Acyclovir 400 mg BID or equivalent.
  - *PCP Prophylaxis:* Final choice of PCP prophyalxis is per investigator discretion.

Final choice of PCP and anti-viral prophylaxis therapy is per investigator discretion. If PCP or anti-viral therapy is not tolerated, alternate to a different PCP or anti-viral therapy, reduce the dose or modify the schedule for the prophylactic agent, or discontinue prophylaxis at investigator discretion.

• *Pre-medications:* None

Umbralisib will be stored in the Moffitt Investigational Pharmacy Department. It will be dispensed at the site by the clinical research staff under the direction of the PI or by a pharmacist at the site. Patients must be provided drug in its original container. Patients should be instructed to return all empty and partially filled bottles including any unused tablets when they return the site. Any unused study drug will be destroyed on site per Investigational Pharmacy standard procedures. Study drug compliance should be reviewed with the patient at the beginning of each new treatment cycle and as needed. Missed doses will be documented in the patients' medical record.

Umbralisib will be self-administered (by the patient). Tablets should be taken at approximately the same time each day with food (within 30 minutes of a meal). Patients should be instructed to swallow the tablets whole and should not chew or crush them.

If a dose of umbralisib is missed, it should be taken as soon as possible on the same day. If it is missed for greater than 12 hours, it should not be replaced. If vomiting occurs, no attempt should be made to replace the vomited dose.

#### 6.2.1.1 DISPENSING OF UMBRALISIB

Before dispensing, the site pharmacist or his/her representative must check that the umbralisib is in accordance with the product specifications and the validity is within the re-test date.

The exact dose and the date of administration of umbralisib must be recorded within the patient's medical records. Any error in drug administration should be recorded (e.g., missed dose).

The Investigational Pharmacist or his/her representative should complete the accountability record with information concerning the dispensation of umbralisib.

If a subject requires a dose reduction, the site pharmacist will dispense only the number of bottles of study drug required for the subject to have an adequate supply until the next dispensing visit.

#### 6.2.2 CRITERIA FOR ONGOING TREATMENT

Continue treatment as per protocol provided that patient has:

- No intolerable toxicities related to study drug.
  - Treatment may be delayed to recover from toxicity for a maximum of eight weeks. Treatment delays of greater than 8 weeks may be allowed after discussion with the Principal Investigator.
- No clinical or radiographic evidence of disease progression.
- Not withdrawn from the study for other reasons.

#### 6.3 DOSING DELAYS AND MODIFICATIONS

Patients should be assessed clinically for toxicity at each visit using the NCI CTCAE v5.0 (http://evs.nci.nih.gov/ftp1/CTCAE/CTCAE) grading scale. Dose delay and/or modification guidance is for adverse events considered at least possibly related to the study drug. If cytopenias are deemed related to the underlying disease rather than study drug, dose modifications are not required, or are per investigator discretion.

Umbralisib should be discontinued if treatment is delayed for greater than 8 weeks due to toxicity unless the Principal Investigator approves restarting treatment. If the subject discontinues treatment but has not progressed, the subject should be followed for progression. If a patient withdraws consent or has documented progression, an end of study visit should be completed.

#### 6.3.1 DOSE DELAY/MODIFICATIONS: UMBRALISIB

#### TABLE 2: UMBRALISIB DOSE DELAY AND/OR MODIFICATIONS GUIDANCE

| NCI-CTCAE Grade   | Dose Delay and/or Modification   |  |  |  |  |  |  |
|---|--|--|--|--|--|--|--|
|   | Hematologic Adverse Event  |  |  |  |  |  |  |
|   | Neutropenia  |  |  |  |  |  |  |
| Grade ≤ 2 neutropenia   | Maintain current dose. Consider supportive care as warranted.  |  |  |  |  |  |  |
| Grade 3 neutropenia   | Maintain current dose, consider supportive care. If neutropenia recurs or persists at Grade 3 for more than 14 days, stop umbralisib until grade ≤ grade 2 and resume at next lower dose level.  |  |  |  |  |  |  |
| Grade 4 neutropenia or
occurrence of neutropenic fever
or infection | 
 
Delay umbralisib until Grade ≤ 3 and/or neutropenic fever or infection is resolved; thereafter, resume at full dose. Consider supportive care. If delay is >8 weeks, permanently discontinue umbralisib.
 
If recurrence after rechallenge, resume at next lower dose level.
 
 |  |  |  |  |  |  |
|   | Thrombocytopenia   |  |  |  |  |  |  |
| Grade ≤ 3 thrombocytopenia  | Maintain current dose level and provide supportive care as clinically warranted.   |  |  |  |  |  |  |
| Grade 4 thrombocytopenia  | Delay umbralisib until Grade $\leq$ 3; thereafter, resume at full dose. Consider supportive care intervention as warranted. If recurrence after rechallenge, resume at next lower dose level. If delay is > 8 weeks, permanently discontinue umbralisib.   |  |  |  |  |  |  |
|   | Pulmonary & Related Infections*  |  |  |  |  |  |  |

| Stop all therapy and hold until complete resolution. Restart umbralisib at one  |
|---|
| lower dose level. If recurrence after rechallenge, discontinue all treatment therapy.   |
| If delay is $> 8$ weeks, permanently discontinue umbralisib.  |
|   |
|   |
|   |
| Discontinue all therapy   |
| ctions clearly not related to immune-mediated pneumonitis, umbralisib may be
s discretion. While pneumonitis has been minimal with umbralisib, it is a reported  |
| with other PI3K delta inhibitors. Use of anti-pneumocystis and anti-herpetic vira   |
| or to starting umbralisib.
Diarrhea and/or Colitis   |
| Maintain current dose level if tolerable or hold and then resume at current dose  |
| level once has resolved.  |
| NOTE : If persistent Grade 2 diarrhea, despite supportive care, delay umbralisil   |
| until $\leq$ Grade 1. If recurrence after rechallenge, resume at next lower dose level.   |
|   |
| If delay is > 8 weeks, permanently discontinue umbralisib.  |
|   |
|   |
| Withhold umbralisib until Grade $\leq 2$ .  |
| If recurrence after rechallenge, resume at next lower dose level.   |
| If delay is > 8 weeks, permanently discontinue umbralisib.  |
| in delay is > 0 weeks, permanently discontinue unioralisib.   |
|   |
|   |
| Hold umbralisib. Treat with supportive care and after resolution of colitis, resume   |
| umbralisib at next lower dose level   |
| If delay is > 8 weeks, permanently discontinue umbralisib.  |
|   |
|   |
| SGPT, AST/SGOT, Bilirubin, Alkaline Phosphatase)
Maintain current umbralisib dose.   |
| Assess concomitant medications and risk   |
| factors*. Monitor labs every 1-2 weeks.   |
| Maintain current umbralisib dose.
Assess concomitant medications and risk factors*.  |
|   |
| Begin supportive care (prednisone $0.5-1.0 \text{ mg/kg/day}$ or equivalent   |
| Begin supportive care (prednisone 0.5-1.0 mg/kg/day or equivalent per investigator discretion) **.  |
| Begin supportive care (prednisone 0.5-1.0 mg/kg/day or equivalent
per investigator discretion) **.
Monitor labs at least weekly until Grade 1.  |
| per investigator discretion) **.  |
| per investigator discretion) **.
Monitor labs at least weekly until Grade 1.
Once resolved to Grade ≤1, taper prednisone by 10 mg per week until off.   |
| per investigator discretion) **.
Monitor labs at least weekly until Grade 1.   |
| 
 
per investigator discretion) **.
 
Monitor labs at least weekly until Grade 1.
 
Once resolved to Grade ≤1, taper prednisone by 10 mg per week until off.
 
If liver toxicity recurs to Grade 2: 
 
Re-initiate steroids.
 
Monitor labs at least weekly until Grade 1.
 
 
 
   |
| 
 
per investigator discretion) **.
 
Monitor labs at least weekly until Grade 1.
 
Once resolved to Grade ≤1, taper prednisone by 10 mg per week until off.
 
If liver toxicity recurs to Grade 2: 
 
Re-initiate steroids.
 
Monitor labs at least weekly until Grade 1.
 
Consider delaying umbralisib.
 
 
 
  |
| 
 
per investigator discretion) **.
 
Monitor labs at least weekly until Grade 1.
 
Once resolved to Grade ≤1, taper prednisone by 10 mg per week until off.
 
If liver toxicity recurs to Grade 2: 
 
Re-initiate steroids.
 
Monitor labs at least weekly until Grade 1.
 
Consider delaying umbralisib.
 
Once resolved to Grade ≤1
 
 
 
   |
| 
 
per investigator discretion) **.
 
Monitor labs at least weekly until Grade 1.
 
Once resolved to Grade ≤1, taper prednisone by 10 mg per week until off.
 
If liver toxicity recurs to Grade 2: 
 
Re-initiate steroids.
 
Monitor labs at least weekly until Grade 1.
 
Consider delaying umbralisib.
 
 
 
  |
| 
 
per investigator discretion) **.
 
Monitor labs at least weekly until Grade 1.
 
Once resolved to Grade ≤1, taper prednisone by 10 mg per week until off.
 
If liver toxicity recurs to Grade 2: 
 
Re-initiate steroids.
 
Monitor labs at least weekly until Grade 1.
 
Consider delaying umbralisib.
 
Once resolved to Grade ≤1
 
If umbralisib was delayed, restart umbralisib at current dose.
 
 
 
 |
|   |

| Grade ≥ 3  | Delay umbralisib.
Assess concomitant medications and risk factors*.
Begin/continue supportive care (prednisone 0.5-1.0 mg/kg/day or equivalent
per investigator discretion) **.
Monitor labs at least weekly until Grade 1.
Once resolved to Grade ≤1:
○ Restart umbralisib at one lower dose level.
○ Taper prednisone by 10 mg per week until off.
If umbralisib is delayed for > 8 weeks, permanently discontinue umbralisib |  |
|--|---|--|
| * Assess for disorders of lipids and glucose, thyroid disorders, alcohol use, viral infections, etc.   |   |  |
| **Supportive Care – Aggressive management of lipid, glucose, other metabolic disorders, viral infections, etc.
Important: Before initiating steroids, check for viral hepatitis or CMV infection. |   |  |
| All Other Non-Hematological Adverse Events   |   |  |
| Grade ≤ 2  | Maintain current dose level   |  |
|  | Withhold umbralisib until Grade $\leq 2$ .
If recurrence after rechallenge, resume at the next lower dose level.   |  |
| Grade ≥ 3  | If delay is > 8 weeks, permanently discontinue umbralisib.  |  |

#### TABLE 3: STUDY DRUG DOSE LEVELS

| Study Drug | Starting Dose | 1 st Dose Reduction | 2 nd Dose Reduction |
|------------|---------------|--------------------------------|--------------------------------|
| Umbralisib | 800 mg        | 600 mg                         | 400 mg                         |

A maximum of two dose level reductions are allowed for umbralisib. If a patient requires a dose reduction of umbralisib due to study drug related toxicity, the dose may not be reescalated. If further evaluation of the toxicity reveals the event was not related to umbralisib, this should be recorded in the medical record and dose re-escalation to the next higher dose level may be considered at the discretion of the investigator.

#### 6.4 ORDERING UMBRALISIB

Umbralisib is available from TG Therapeutics. Please allow 5 to 7 business days between drug ordering and drug arrival. Please direct drug orders to [contact]. The email should include the following:

- Requested quantity of TG Therapeutics study drug(s)
- Principal Investigator name
- Study title
- Investigational drug pharmacy shipping address

Upon receipt of treatment supplies, the Pharmacist or the appropriate person of the site should update the accountability forms for umbralisib. If any abnormality on the supplied bottles (umbralisib) is observed, the Pharmacist or the appropriate person must document that on the acknowledgement of receipt and contact TG Therapeutics.

#### 6.5 DURATION OF THERAPY

In the absence of treatment delays due to adverse event(s), treatment should continue through Cycle 1 and beyond unless one of the following criteria applies:

- Disease progression or inter-current illness that prevents further treatment.
- Patient decides to withdraw from the study, or changes in the patient's condition render the patient unacceptable for further treatment in the judgment of the investigator.
- Study drug will be made available to responding patients until disease progression. If umbralisib becomes commercially available during the active period on study, an attempt will be made to obtain this agent through commercial insurance. If study drug continues past cycle 12, any laboratory or other testing procedures will be ordered at physician discretion and not considered a study procedure. Adverse events will be collected during this time, per guidance in Section 10.4.3.

During the study period, all patients will be evaluated for response by CT or MRI within 14 days prior to Cycle 4, Day 1 for Cycle 3 assessment, and within 14 days prior to Cycle 13, Day 1 for Cycle 12 assessment, and at any other time point to confirm progression. Patients who fail to achieve a partial or complete response to umbralisib at the Cycle 3 assessment will discontinue study treatment. At that time, patients- will be provided appropriate options to receive established frontline therapy. Patients who demonstrate a partial or complete response will be treated until disease progression, unacceptable toxicity, or the end of the study.Patients who discontinue from study treatment and have not progressed should continue to be followed for progression, if agreeable, approximately every 3 months. If the patient discontinues after Cycle 12 for reasons other than disease progression, they should continue to be followed for progression approximately every 6 months.

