#### 4.4 DISCONTINUATION FROM STUDY TREATMENT

Patients will be discontinued from study treatment for any of the following reasons:

- Disease progression
- Failure to achieve a partial or complete response to umbralisib at the Cycle 3 assessment
- Intolerable toxicity related to study drug
- Patient requests to withdraw consent or discontinue treatment
- Pregnancy
- Inability of the patient to comply with study requirements
- Conditions requiring therapeutic intervention not permitted by the protocol
- Non-compliance/lost to follow-up
- Investigator discretion
- Discontinuation of the study

Patients who discontinue from study treatment prior to Cycle 12 (for reasons other than progressive disease) should continue to be followed for progression approximately every 3 months up until the time Cycle 12 would have occurred, then approximately every 6 months.

Patients who discontinue from study treatment after Cycle 12 for reasons other than disease progression should be followed for progression approximately every 6 months.

After withdrawal from protocol treatment, patients should be followed for AEs for 30 calendar days after their last dose of study drug. All new AEs occurring during this period must be reported and followed until resolution, unless, in the opinion of the investigator, these values are not likely to improve because of the underlying disease. In this case the investigators must record his or her reasoning for this decision in the patient's medical records.

All patients who have CTCAE Grade 3 or 4 laboratory abnormalities at the time of withdrawal should be followed until the laboratory values have returned to Grade 1 or 2, unless in the opinion of the investigator, it is not likely that these values are to improve because of the underlying disease. In this case, the investigator must record his or her reasoning for making this decision in the patient's medical records.

All patients that begin therapy outside of the scope of this protocol within 30 days of discontinuing umbralisib do not need to be followed for AEs, unless umbralisib is determined to be the direct cause of the AE in the opinion of the treating investigator. After 30 days from discontinuation of umbralisib, these AEs no longer need to be followed.

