| PDs    |                | Х         |        |              |          | Х              |  |           |            |            |
| Umbralisib 800 mg  |                |           |        |              | Daily    | 7 Days 1 – 28  |  |           |            |            |
| Bone Marrow Biopsy                            | Х              |           |        |              |          |                | Х  |           |            |            |
| AE Assessment  |                | Х         |        | Х            | Х        | Х              | Х  | Х         |            |            |

 Visit days and all related assessments and testing have +/- 1 day window in Cycle 1.

 Unless otherwise noted (i.e. CT scans), visit days and all related assessments and testing have +/- 3 day window in Cycles 2 - 6.

 Unless otherwise noted (i.e. CT scans), visit days and all related assessments and testing have +/- 7 day window for Cycles > 6.

 Serum virology to include HBsAg, HBc antibody, HCV antibody, CMV IgG and CMV IgM. If HBc antibody is positive, the subject must be evaluated for the presence of HBV DNA by PCR - See Appendix C. If HCV antibody is positive, the subject must be evaluated for the presence of HCV RNA by PCR. If the subject is CMV IgM positive, the subject must be evaluated for the presence of CMV DNA by PCR. CMV surveillance by PCR every 3 cycles while receiving study treatment. In addition, a final CMV test by PCR should be done upon treatment discontinuation.

 Baseline CT scan within 30 days prior to Cycle 1, Day 1; then within 14 days prior to Cycle 4, Day 1 for Cycle 3 assessment, and within 14 days prior to Cycle 13, Day 1 for Cycle 12 assessment. Additional scans may be requested at the discretion of the investigator at any other time point to confirm progression (all scans +/-14 days). CT imaging should be performed at EOT visit if it hasn't been completed within past 30 days.

 Serum pregnancy test within 3 days prior to starting treatment on Cycle 1, Day 1 for women of childbearing potential.

 Peripheral Blood Mononuclear Cells (PBMC) – Peripheral blood sample to be obtained pre-dose on C1D1, C2D1, C4D1, C7D1, C13D1 and at the time of disease progression, which may occur at any time point including at the End of Treatment visit or the End of Study visit.

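### Sections 5 and 6.5 contradict each other on whether patients still on umbralisib after Cycle 12 have study progression assessments, so the schedule behind late PFS and DOR is undefined

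*Combined protocol and SAP*

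**What the plan says.** **On drug after Cycle 12.** Section 6.5 states that, for drug continued beyond Cycle 12, "any laboratory or other testing procedures will be ordered at physician discretion and not considered a study procedure". Only adverse event collection is kept. The Section 5 table has a column for cycles beyond Cycle 6, repeated every 3 cycles with no upper limit. It marks physical examination, hematology, chemistry, response assessment and CMV surveillance. Footnote 4 of that table asks for "CMV surveillance by PCR every 3 cycles while receiving study treatment", again with no stop at Cycle 12, and Section 5.1.1 (local laboratory assessments, item 4) repeats it.

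**Imaging.** After baseline, footnote 5 dates two scans, one before Cycle 4 Day 1 and one before Cycle 13 Day 1. It adds a CT at end of treatment if none was done in the previous 30 days. Beyond that, "Additional scans may be requested at the discretion of the investigator at any other time point to confirm progression".

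**Off drug without progression.** For patients who stop after Cycle 12, Section 4.4 says they "should be followed for progression approximately every 6 months", and Section 6.5 agrees. For those who stop before Cycle 12, Section 4.4 gives "approximately every 3 months up until the time Cycle 12 would have occurred, then approximately every 6 months". Section 6.5 says they "should continue to be followed for progression, if agreeable, approximately every 3 months", with no later switch to 6 months.

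**Use of the data.** Section 9.9.1 calls PFS one of two primary efficacy outcomes, although Section 2.1 lists it as a secondary objective. PFS is to be estimated by Kaplan-Meier and tested with a one-sided one-sample log-rank test. No null median is given. Section 9.1 plans about 18 months of accrual and 24 months of follow-up.

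**The concern.** A progression time is known only as well as the schedule that finds it. Kaplan-Meier dates the event at detection, so a longer gap between looks gives a longer apparent PFS. In a randomised trial, delay common to both arms partly cancels. In a single arm tested against a fixed value it does not: late reading leaves fewer observed events against the same expected number, which favours the drug.

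If 6.5 is followed as written, patients on drug after month 11 have no stated interval, and a negative assessment need not be recorded. Off-drug patients have a stated interval of about 6 months. How an event is found would then depend on whether the patient is still taking umbralisib. DOR ends on the same event, so it inherits the problem. Section 8.4 lets imaging override physical examination, and isolated lymphocytosis does not count as progression, so late events may turn on scans that are discretionary.

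**Working it through.** **The plan's own figure.** The only design calculation is for ORR: stop at 18 or fewer responses in 27, succeed at 25 or more in 35, with response rates of 0.60 and 0.80. An exact binomial two-stage calculation gives a type I error of 0.0965 and power of 0.9003, and a search confirms this as the minimax design. A patient must be in PR or CR at the Cycle 3 assessment to stay on drug, so anyone on drug past Cycle 12 is already a responder. The conflict therefore does not touch the ORR rule. No event count or power is stated for PFS, so there is no PFS figure to reproduce.

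**When the conflict starts.** 12 × 28 = 336 days; 336 / 30.4375 = 11.04 months.

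**How much of PFS lies beyond it.** The documents give no PFS median for untreated patients. The only CLL figure (Section 1.2.2.1) is 24.0 months, 95% CI 7.4 to not reached, post hoc in 20 relapsed or refractory patients. Assume exponential PFS with median m, so S(t) = 0.5^(t/m):

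| Assumed m (months) | Progression-free at 11.04 months |
|---|---|
| 7.4 | 0.356 |
| 16 | 0.620 |
| 24 | 0.727 |
| 36 | 0.809 |

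The median falls after Cycle 12 only if m exceeds 11.04 months. At m = 24, the share of events up to month 24 that fall after Cycle 12 is (0.727 − 0.500) / (1 − 0.500) = 0.454.

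**One common grid for everyone.** The read median is the first assessment at or after the true median. A 3-cycle grid after 11.04 months has steps of 84 / 30.4375 = 2.76 months; the other grid has steps of 6 months.

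| True median | Read, every 3 cycles | Read, every 6 months |
|---|---|---|
| 16 | 16.6 | 17.0 |
| 20 | 22.1 | 23.0 |
| 24 | 24.8 | 29.0 |
| 30 | 30.4 | 35.0 |

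The jump to 29.0 arises because 24 lies just past the grid point at 11.04 + 12 = 23.04.

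**Mixed reading if 6.5 governs.** Simulation: 35 patients, uniform accrual over 18 months, at least 24 months of follow-up, 4,000 runs. Events before Cycle 12 are read at the two scheduled scans. After that, an assumed 40% are off drug and read every 6 months, and the other 60% are read with a fixed lag. Entries are the typical Kaplan-Meier median among runs that reached it, with the share of runs that did not.

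| True median | No lag | 3 months | 6 months | 12 months |
|---|---|---|---|---|
| 16 | 17.0 (0.2%) | 18.3 (0.1%) | 21.2 (0.3%) | 24.2 (1.4%) |
| 24 | 24.1 (4.6%) | 27.1 (7.3%) | 29.0 (11.0%) | 30.8 (22.2%) |
| 30 | 29.0 (20.3%) | 29.7 (25.6%) | 31.1 (32.2%) | 34.9 (46.6%) |

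In the last row many runs never reach the median, so those entries are pulled down. The 40% equals 1 − 0.60, the non-response share at the null ORR; at 0.80 it would be 20%. The model treats every event as found by assessment. Deaths are dated exactly, so the shift is smaller to the extent that events are deaths.

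**Early stoppers.** The intervals in 4.4 and 6.5 agree until Cycle 12 would have occurred. After that they are about 6 and about 3 months, a factor of two.

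**The case against.** The documents do not leave on-drug patients unobserved. The Section 5 table still marks response assessment every 3 cycles. Section 6.2.2 lets treatment continue only without clinical or radiographic evidence of progression, Section 6.2.1 has compliance reviewed at each new cycle, and evaluation to confirm progression is allowed at any time. The go/no-go decision rests on ORR alone, and dating progression at detection is conventional. All of this stands, and it rules out several stronger readings:

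- A reader might infer that no study assessment exists after Cycle 12. What the text shows is two provisions that conflict.
- A reader might infer that responders on drug are assessed least often. Physician discretion is not a lower frequency, and if Section 5 governs they are seen about every 12 weeks, roughly twice as often as off-drug patients.
- A reader might infer a definite upward bias. With prompt on-drug detection the read median is 24.1 against a true 24, and the 6-monthly off-drug grid itself delays reading.
- A reader might take the 36 weeks (8.3 months) between the two planned scans as part of this gap. That interval ends at Cycle 12, and examinations and blood counts continue through it.

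None of this removes the contradiction. It limits what can be said about the direction and size of its effect.

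**Conclusion.** The contradiction between Sections 5 and 6.5 is established from the text, as is the different interval for early stoppers in 4.4 and 6.5. The effect on PFS and DOR is conditional on 6.5 being followed. It then depends on a lag that the documents leave open: at a true median of 24 months with 40% off drug, the read median runs from about 24 to about 31 months as the lag goes from 0 to 12 months. That range rests on an exponential shape, an assumed off-drug share and assumed lags. It borrows its median from a small post hoc relapsed/refractory group, so a median after Cycle 12 in untreated patients is plausible but not shown; at 7.4 months it falls before. The ORR design stands. This should be corrected because Section 9.9.1 gives PFS a formal single-arm test, but it does not undermine the trial's main decision.

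**What to change.** 1. Reconcile Section 6.5 with Section 5 so that the response assessments already in the Section 5 table are recorded as study data for patients on drug, until progression or the end of follow-up. Record negative assessments with their dates: without them the last progression-free date is unknown.
2. State one progression follow-up interval for patients off drug, in the same words in 4.4 and 6.5.
3. Report an interval-censored (Turnbull) PFS estimate as a sensitivity analysis beside Kaplan-Meier. A common schedule evens out ascertainment but does not remove delay, as the 6-month column above shows.
4. Reconcile the CMV surveillance passages (Section 5 footnote 4, Section 5.1.1 item 4 and Section 6.5). Which one should govern is a clinical matter and is not proposed here.

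The cost is amendment wording, data entry and a little more analysis, with no added scans. Drug is dispensed at the site and compliance is reviewed each cycle, so on-drug patients already have site contact. If visits have in practice lapsed under 6.5, restoring them adds some burden. Imaging after the scan before Cycle 13 Day 1 stays discretionary apart from end of treatment, so some uncertainty about late event times will remain and should be acknowledged when PFS is reported.
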